1	Cognitive Performance Following Caffeinated Chewing Gum in
2	night-shift Emergency Physicians: A Double-blind Randomized
3	Crossover Controlled Trial
4	China Medical University Hospital, Taichung, Taiwan. 404.
5	Document Date: Nov. 13, 2024
6	
7	Project summary
8	This study aimed to examine the impact of caffeinated chewing gum on the cognitive
9	performance of night-shift emergency physicians in a partially sleep-deprived state. A
10	randomized, double-blind crossover controlled experimental design was employed in
11	which fourteen (Age: 29.9 ± 1.44 ; height: 176.5 ± 5.3 ; weight: 78.1 ± 13.4) emergency
12	physicians consumed either caffeinated chewing gum (CAF) containing 200 mg
13	caffeine or a caffeine-free placebo gum (PLA) for 10 minutes at 03:30 am during their
14	first 8-hour night shift after at least one day off, and completed cognitive performance
15	tests before shift, mid-shift (10 minutes after gum chewing), and after shift, including
16	included Corsi block test, Task-switching paradigm, Stroop Test, Visual search, and
17	Wisconsin Card Sorting Task. Sleep quality was assessed subjectively by a single
18	question score, and objectively by ActiGraph for one night on the off day and the last
19	sleep before the first night shift, to evaluate the effect of sleep quality on cognitive

20	performance.
----	--------------

22	Keywords: Reaction time, cognitive function, Stoop test, Visual search, Patient safety
23	
24	
25	
26	

27 Introduction

A substantial body of research has demonstrated that the cognitive function of night shift doctors declines significantly before work [1-4], particularly in the context of the first consecutive night shift [5]; This raises concerns about the potential impact on patient safety. Consequently, there has been a significant focus on night shift scheduling and working hours [6], to identify the most appropriate rotation method and working hours for emergency physicians to ensure patient safety [7].

34 Caffeine is a psychoactive substance found in many drinks and certain foods. The 35 most widely known and consumed source of caffeine is coffee, but caffeine is also found in tea, energy drinks, carbonated soft drinks, fruit, and foods containing cocoa [8, 36 37 9]. It is a recognized stimulant with psychomotor activation and alertness effects [10] 38 and is often consumed by night shift workers, drivers, or the general public. Recent 39 studies have also found that caffeine may reduce the risk of dementia and cognitive 40 decline in the elderly and improve cognitive decline in people with cognitive 41 impairment [11]. Low-dose caffeine's primary mechanism of action as a 42 psychostimulant is based on central antagonism at A1 and A2A adenosine receptors at 43 doses typically consumed orally with caffeinated foods and beverages. Caffeine's ability to bind to adenosine receptors helps to inhibit the brakes exerted by endogenous 44 45 adenosine on the ascending dopamine and arousal systems, thereby enhancing 46 cholinergic and dopaminergic transmission [12, 13]. Thus, caffeine intake helps to improve self-reported energy, mood, and cognitive functions such as attention; it may 47 also improve simple reaction time, choice reaction time, memory, or fatigue [11, 14]. 48

49 The ability of caffeine supplementation to improve cognitive function has been50 studied in several areas. For example, caffeine supplementation was found to be

51	effective in improving visual search and engagement speed in an alert state one hour
52	before a test in e-sports athletes [15], as well as increasing the speed of keyboard
53	tapping [16], increasing reaction time, and improving shot precision in e-sports
54	shooting events [17, 18], and decreasing reaction time in a Stroop task [17, 19]. In
55	addition, players in such video games must utilize different control strategies to respond
56	quickly to fast-paced, high-stress visual and auditory stimuli, and they must have
57	autonomy to adapt to changing environments [20]. This is similar to emergency
58	physicians, who must respond quickly to changes in patient conditions in a high-
59	pressure work environment. Zabelina et al., Crawford et al. and Marsden et al. have
60	also shown that caffeine significantly improves problem-solving abilities [21-23].
61	Therefore, emergency physicians, who may be exposed to fast-paced, high-stress visual
62	and auditory stimuli, may be able to find strategies to overcome these challenges by
63	improving their problem-solving abilities through caffeine.
~ ^	

Graham Marsden and John Leach also found that caffeine improved visual search performance in experienced navigators [21], which may also be related to emergency physicians' ability to search for lesions on diagnostic clues and medical images. In addition, caffeine has been shown to improve performance and cognitive functioning in shift workers in a review of the literature [24]. In recent years, caffeine chewing gum has been marketed to facilitate and accelerate caffeine intake [25], and studies have

70	examined the effects of caffeine gum on cognitive performance in e-sports players [17].
71	However, no studies have been conducted on the effects of caffeine supplementation on
72	cognitive functioning in night-shift emergency physicians with caffeinated chewing
73	gum.
74	This study aims to investigate whether caffeine supplementation with caffeinated
75	chewing gum can be used by emergency physicians during night shifts to maintain
76	proper cognitive functioning and thus patient safety. At the same time, sleep monitoring
77	was performed to observe whether caffeine supplementation affected subsequent sleep.
78	This is to provide emergency physicians with a reference for caffeine supplementation
79	with caffeine gum during night shift work.
80	
81	2. Methods
82	2.1. Design
83	This experiment was a double-blind, repeated-measures, crossover design
84	according to the guidelines of CONSORT 2010[26] and was divided into either a
85	caffeine trial (CAF) or a placebo trial (PL). To eliminate the impact of individual
86	physical differences, a crossover trial was conducted with the same group of subjects.
87	Randomized groups were created using Microsoft 365-Excel (Microsoft, Redmond,
88	Washington, United States), and allocation was randomized and unpredictable. Each

89	trial was separated by at least four weeks to avoid interactive effects. This study
90	compared CAF and PL trial to determine the effects of caffeinated chewing gum on
91	cognitive performance in emergency physicians engaged in night shift work., and
92	subjective, objective sleep quality. Caffeinated chewing gum and placebo chewing gum
93	are very similar in appearance, color, size, shape, and flavor and are difficult to
94	distinguish. The randomization was carried out by a research assistant, with another
95	resident performing the experiment, and neither the subjects themselves nor the resident
96	experimenting knew which group the subjects were assigned to or what type of gum
97	they were assigned. Once the data has been collected, it will be forwarded to the group's
98	statistical analyst for statistical analysis, who was also unaware of the group
99	assignments. At least one week before the formal experiment, all subjects participated
100	in three to five familiarization tests for the cognitive function tests. Sleep quality was
101	also assessed subjectively by a single question score, and objectively by ActiGraph for
102	one night on the off day and the last sleep before the first night shift. The primary
103	outcome was the results of cognitive function tests, and the secondary outcome was the
104	sleep quality.

106 2.2. Participants

107 Fourteen healthy male emergency physicians were recruited in this study and

based on previous research on caffeine in e-sport athletes [17, 18], we used the G*power 108 3.1 software 24 to achieve an alpha value of 5% and a power of 0.8, which was 109 110 sufficient for the study with only six subjects. However, due to the lack of relevant studies on the effects of caffeine and caffeinated chewing gum on cognitive functioning 111 in night-shift healthcare workers, reference was made to a recent study that examined 112 the cognitive performance of emergency physicians after 24 consecutive hours of on-113 call duty, which included 13 subjects [3]. Therefore, it should be adequate to interpret 114 115 the data derived and statistics from the study.

116 All participants had experience working regular rotating shifts on the emergency clinical front line and regularly accepted night shift assignments each month. The 117 118 inclusion criteria were: (i) healthy male adults, those individuals who are free of pain, 119 insomnia, or other injuries recently, without any medication used in recent 2 months, (ii) underwent rotating shifts on the emergency clinical front line with regularly 120 accepted night shift more than two years. The exclusion criteria were: (i) allergy to 121 caffeine, (ii) experience of adverse effects of caffeine, (iii) with cardiovascular diseases 122 123 or any disease that made subjects feel ill. Two weeks before the main trial, all the participants were asked to avoid ingestion of more than 80 mg of caffeine a day. Before 124 the experiment, all participants were fully informed of the experimental procedures and 125 126 risks and provided informed consent. This study received approval from the 127 Institutional Review Board of China Medical University Hospital (CMUH111-REC2-

128 169). This study was conducted following the Declaration of Helsinki.

129

130 **2.3. Protocol**

131 **2.3.1.** Experimental procedure

The entire study was conducted in the office of the emergency department of China Medical University Hospital, and the indoor ambient temperature was set at 22°C. Participants' diet and mealtimes were recorded for the 3 days before the first formal experiment, and the participants were required to follow the same diet 3 days before the next formal experiment. They were also required to avoid food and beverages with caffeine (e.g., coffee, energy drinks, chocolate, chocolate drink, and tea) 3 days before the formal experiment.

On the day of the formal experiment, participants had breakfast and lunch at 08:00 and 12:00, respectively. The participants arrived at the office at approximately 23:20 for the experiment. A brief explanation was given and the cognitive test was administered at 23:30, which took about 20 minutes to complete, after which the subjects were ready to go to work. At 03:30, according to the randomized results, the subjects were given two pieces of caffeinated chewing gum at an absolute dose of 200 mg (Military Energy Gum®, Ford Gum and Machine Go, Akron, NY, USA) (CAF trial) 146 or two pieces of similar looking and tasting placebo gum that did not contain caffeine (xylitol, lime mint, green; Lotte, Saitama, Japan) (PLA trial). After 10 minutes of 147 148 chewing, cognitive function tests were administered. Finally, the last cognitive function tests were performed after duty at 08:20. All subjects used a dedicated computer with a 149 screen frame rate of at least 240 Hz and a mouse response rate of 1ms. 150 151 To explore the validity of the blinding method, we asked the participants (before and after the test) to identify the supplements they ingested. To do this, the question 152 was as follows: "Which supplement do you think you ingested?" There are three 153 possible answers to this question: (a) caffeine; (b) placebo; and (c) don't know. 154 155 Furthermore, the occurrence of side effects or complications was recorded during the 156 trial.

157 **2.3.2.** Outcome measure

158 2.3.2.1. Cognitive function tests

159 Subjects were sequentially given five tests: Corsi block test, Task-switching 160 paradigm, Stroop Test, Visual search, and Wisconsin Card Sorting Task. All the above 161 cognitive function tests were conducted using Psych/Lab for Windows. Measures used 162 in the literature have satisfactory reliability and validity[27].

163 **2.3.2.1.1.** Corsi block test

164 There will be 9 purple squares in the screen, when the test starts, it will flash a

165 number of them randomly in yellow color (the more the number increases), then you will hear "Go", then you have to click the order of the flashing ones, and then press 166 "DONE" in the lower right corner. The smiley face means correct, the crying face 167 means wrong. The maximum number of correct answers will be displayed at the end of 168 the test, which is mainly to test the ability of situational awareness and working memory. 169 170 The whole process takes about 2 minutes[28-30].

171

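### Both sleep recordings in the Project summary and section 2.1 come before the 03:30 gum, so the CAF versus PL sleep comparison cannot show whether caffeine affected later sleep

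*Combined protocol and SAP*

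**What the plan says.** **Aim and role of sleep**
- Introduction, closing paragraph: sleep monitoring "was performed to observe whether caffeine supplementation affected subsequent sleep". The paragraph then offers the results to emergency physicians as guidance on using the gum on night shifts.
- Section 2.1 Design: the study "compared CAF and PL trial to determine the effects of caffeinated chewing gum on" cognitive performance, and the same sentence goes on to list subjective and objective sleep quality.
- Section 2.1, end: the primary "outcome was the results of cognitive function tests, and the secondary outcome was the" sleep quality.

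**When sleep is recorded**
- Project summary: the gum is chewed during the "first 8-hour night shift after at least one day off, and completed cognitive performance" tests before, during and after that shift. Sleep is assessed on one off-day night and on the last "sleep before the first night shift, to evaluate the effect of sleep quality on cognitive" performance.
- Section 2.1 names the same two sleeps: "one night on the off day and the last sleep before the first night shift. The primary" (the final two words open the next sentence).
- Section 2.3.2.2 also gives two sleep periods, but it places the second before a duty that carries two ordinals at once, first and third. It calls the 0-10 rating daily without listing days.

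**Clock times, section 2.3.1**
- "The participants arrived at the office at approximately 23:20 for the experiment".
- "At 03:30, according to the randomized results, the subjects were given" the gum.
- The last cognitive battery is at 08:20, after duty.

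**The concern.** An outcome recorded before an exposure cannot respond to it. The plan declares an interest in sleep after the gum and makes sleep the secondary outcome, but the sleeps it names in two places both lie on the wrong side of 03:30.

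If the comparison is run and reported as planned, either result misleads. A non-significant difference would read as evidence that caffeine gum late in a night shift leaves daytime sleep intact, although the data contain no information on that question. A significant difference would be chance or a pre-treatment imbalance, yet it would be presented as an effect of the gum. Because the Introduction offers the findings as practical guidance, false reassurance is the likelier harm. No analysis of the existing windows can repair this.

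**Working it through.** The plan gives no sleep effect size and no power figure for sleep, so there is nothing of its own to reproduce. The check orders the stated times and then asks what the test can detect.

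**1. Timeline around the gum**

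| Event | Source | Relative to 03:30 |
|---|---|---|
| Off-day night | Project summary, 2.1 | before (undated; see below) |
| Final sleep ahead of the first night shift | Project summary, 2.1 | ends by 23:20 at the latest |
| Arrival, about 23:20 | 2.3.1 | 4 h 10 min before |
| First battery, 23:30 | 2.3.1 | 4 h 00 min before |
| Gum, 03:30 | Project summary, 2.3.1 | 0 |
| Last battery, 08:20 | 2.3.1 | 4 h 50 min after |
| Battery ends, about 08:40 (about 20 minutes, from 2.3.1) | 2.3.1 | 5 h 10 min after |
| First main sleep after the gum | not scheduled | 5 h 10 min or more after |

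The off day carries no date. The shift is described as the first after at least one day off, and the Project summary treats sleep as a factor acting on cognition. Both point to an off day before the shift.

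**2. The alternative reading of section 2.3.2.2**

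Suppose the third duty was meant, nights are consecutive and clock times repeat. The recorded sleep then falls between 08:20 after duty 2 and 23:20 before duty 3.
- 03:30 to 08:20 the next day: 24 h + 4 h 50 min = 28 h 50 min.
- 03:30 to 23:20 the next day: 24 h + 19 h 50 min = 43 h 50 min.

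That sleep follows the gum, but it is not the first sleep after it and it also follows another night shift.

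**3. What the test can detect on the schedule in the Project summary and section 2.1**

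Let D be the within-person CAF minus PL difference in a sleep index recorded before the gum. With randomized order and no carry-over across the gap of at least four weeks, E(D) = 0 whatever caffeine does to later sleep. A paired test at alpha 0.05 therefore rejects with probability 0.05 per index.

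Section 2.3.2.2 lists eight ActiGraph indices plus one rating. Over two sleeps that is 9 × 2 = 18 possible comparisons. If all were tested, the chance of at least one false rejection would lie between 5% (fully correlated) and 1 − 0.95^18 = 60% (independent).

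**4. What the same 14 physicians could show if the first post-shift sleep were recorded**

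Paired t test, n = 14, df = 13, two-sided alpha 0.05 (the plan does not state sidedness). Power = P(|T| > t(0.975, 13)), where T is noncentral t with noncentrality dz × √14 and √14 = 3.742. Here dz is the mean difference divided by the SD of the differences. The dz values are assumptions.

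| Assumed dz | Noncentrality | Power, post-gum sleep | Rejection rate, pre-gum sleep |
|---|---|---|---|
| 0.5 | 1.87 | 0.410 | 0.05 |
| 0.8 | 2.99 | 0.790 | 0.05 |
| 1.0 | 3.74 | 0.932 | 0.05 |

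Power reaches 80% at dz = 0.81.

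**The case against.** The best defence is that the schedule is not settled. Section 2.3.2.2 is the only section devoted to sleep measurement, and its wording could mean a sleep before the third duty, which follows the gum. The off day is undated, and a daily rating could include the post-shift sleep. This stands as a reason to reconcile the text before labelling any data pre-exposure. It does not rescue the aim: no section places a recording or rating on the first sleep after the gum, and the third-duty reading contradicts two other sections.

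Second, the Project summary gives a purpose that the windows do suit, namely how sleep quality bears on cognitive performance. That is true, and it means the data have a use. It does not remove the subsequent-sleep aim in the Introduction or the mention of sleep in the section 2.1 comparison.

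Third, the Statistical analysis section assigns the paired t test to the cognitive measures and no test to sleep by name. Pre-shift sleep could properly sit among the baseline comparisons. Also true, but section 2.1 lists sleep among the effects of the gum to be determined, and the argument applies to whatever test is used.

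Finally, the power figures rest on assumed effects and do not size the defect. Agreed: they show only that recording the right sleep would be worthwhile for large effects and weak for moderate ones.

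**Conclusion.** The concern holds for the schedule in the Project summary and section 2.1. The latest recorded sleep ends at least 4 h 10 min before the gum. The first sleep that caffeine could affect starts about 5 h 10 min or more after it and has no scheduled recording. The CAF versus PL sleep comparison therefore carries no information on the stated aim and rejects at 5% per index regardless of the true effect.

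This rests on three assumptions: the off day precedes the shift, there is no carry-over across at least four weeks, and section 2.3.2.2 does not mean the third duty. If the last is wrong, a later and confounded sleep was recorded, and the first post-gum sleep is still missed. The primary cognitive outcome is not affected. The matter must be fixed because a declared aim and the treatment comparison on the secondary outcome cannot be answered as scheduled.

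**What to change.** 1. **First, settle the schedule.** Date the off day relative to the shift, list the days on which the 0-10 item is asked, and reconcile the second recording in section 2.3.2.2 with the Project summary and section 2.1.
2. **If data collection is open:** in each period, record the first sleep after the 08:20 battery with the ActiGraph and the 0-10 item. Make that sleep the secondary outcome, compared CAF versus PL within person. Cost: one more sleep period of device wear and one more rating per condition, with no extra participants.
3. **If collection is complete and step 1 confirms that both sleeps preceded the gum:** remove the subsequent-sleep aim from the Introduction and sleep from the gum effects in section 2.1. Label the sleep data pre-exposure, and use them only as baseline or descriptive data for the purpose in the Project summary. Cost: wording only.
4. **If step 1 shows that a later sleep was recorded:** say which one, and do not present it as the first sleep after the gum.

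The mainly past-tense methods and the reported age, height and weight of the fourteen physicians suggest that enrolment is finished, although section 2.1 still speaks of data to be forwarded. The sponsor should state which case applies.

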2.3.2.1.2. Task-switching paradigm

There are two shapes (circle, square) and two colors (yellow, blue), four 172 combinations in total. At the beginning of the test, you will see "SHAPE" or "COLOR" 173 (which means that the answer to the question will be based on the shape or color), and 174 175 then a colorful pattern (e.g., yellow square or blue circle) will appear, then answer the 176 question according to the answer you have just seen (shape or color) as soon as possible. Press B for circles, N for squares, B for yellow, N for blue, and finally the average 177 reaction speed is displayed, which is a test of cognitive structure, flexibility, and 178 plasticity in task processing. The whole test takes about 4 minutes[31, 32]. 179

180

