2.3.2.1.3. Stroop Test

In this quiz, you will see different colors for different words, but all the answers 181 are based on the colors (no matter what the words are). Press R for red, G for green, B 182 for blue, and Y for yellow; for example, if you see "green in red color", you have to 183

184 press R. The test results comprised a congruent condition, in which the key pressed 185 corresponded correctly to the color on the screen, and an incongruent condition, in 186 which the key pressed corresponded incorrectly to the color name on the screen. At the 187 end of the test, the reaction time will be displayed, which is mainly a test of the ability 188 to inhibit cognitive interference. The whole test takes about 5 minutes[33, 34].

189 **2.3.2.1.4.** Visual search

In the visual search test, participants identified orange "T" s on the screen from upside-down orange "T" s, blue "T" s, and upside-down blue "T" s. When an orange "T" would appear, the participants were required to press the spacebar as quickly as possible. If no orange "T" appeared, the participants were required to not react. The test contains 80 search displays, each containing 5, 10, 15 and 20 items, mainly to test the search ability of dynamic vision. Reaction speed was displayed at the end of the test, and the whole test took about 4 minutes[15, 21, 35].

197 **2.3.2.1.5.** Wisconsin Card Sorting Task

There is a trial-and-error component to this test. You have to answer the questions first and then determine what the question is based on what is right or wrong. The test is presented in a matching mode, where a pattern on the left is matched with one of the four patterns on the right, and the matching criteria are color, shape, and number. During the test, the questions will be changed from time to time, so if you find out the rules and then suddenly get a question wrong, it means that the question has been changed.
The number of errors is displayed at the end of the test to help measure a person's ability
to reason abstractly and to change problem-solving strategies when necessary. The
entire test lasted about 4 minutes[36-38].

207

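### Five cognitive tests at two post-gum times share the primary outcome at a single 0.05 level, with no lead test, time point, success rule, multiplicity control or designated primary analysis

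*Combined protocol and SAP*

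**What the plan says.** The endpoint statement in section 2.1 (Design) is that the primary "outcome was the results of cognitive function tests, and the secondary outcome was the" sleep quality. It ranks no test above another.

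Section 2.3.2.1 lists the battery: "Subjects were sequentially given five tests: Corsi block test, Task-switching" paradigm, then Stroop, visual search and Wisconsin card sorting. Section 2.3.1 has the battery run before the shift, again after ten minutes of chewing from 03:30, and once more at the end: "Finally, the last cognitive function tests were performed after duty at 08:20". Two of the three sittings therefore follow the gum, and neither is called the main one.

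The scores differ by test:

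- Corsi (2.3.2.1.1): "The maximum number of correct answers will be displayed at the end of" the test.
- Task-switching (2.3.2.1.2): the average "reaction speed is displayed, which is a test of cognitive structure", among other abilities.
- Stroop (2.3.2.1.3): two conditions, "The test results comprised a congruent condition, in which the key pressed" matching the colour, and an incongruent one.
- Visual search (2.3.2.1.4): "Reaction speed was displayed at the end of the test".
- Card sorting (2.3.2.1.5): "The number of errors is displayed at the end of the test".

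The Statistical analysis section assigns a paired t test to cognitive performance, accuracy and hit reaction time. It assigns a 2 × 2 mixed-design repeated-measures ANOVA to the effects of the intervention. It does not tie accuracy or hit reaction time to particular tests, give the time point for the t test, or name the ANOVA factors. One significance level, 0.05, covers everything.

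**The concern.** A primary outcome should let a reader decide from the plan alone whether the trial met it. Here several results could each be presented as the primary finding: any of five tests, at either of two times, by either of two analyses. If one significant result is enough, the stated 5% no longer describes the chance of wrongly claiming a caffeine effect. A reader of the eventual report could not tell whether a positive Stroop result at 03:40, say, was the planned primary result or one of several chances.

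This matters because the Introduction sets a broad aim: whether the gum can maintain cognitive functioning on night shifts, and so patient safety. A claim of that breadth needs a stated rule for when it is supported.

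**Working it through.** **Does any other part of the plan supply the missing rule?**

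- The sample-size paragraph (section 2.2) gives alpha 5%, power 0.8 and six subjects. It gives no outcome or effect size, so the six cannot be reproduced and do not point to a lead test.
- The ANOVA does not settle the matter. The design is two gums by three times, all within subject; a 2 × 2 layout cannot hold all three times, and the section does not say which are used.
- No hierarchy, composite or correction appears in the rest of the text.

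**Inputs.** Five tests and two post-gum times (2.3.1, 2.3.2.1); n = 14 (2.2); alpha 0.05 (Statistical analysis). Assumed: two-sided tests, no caffeine effect on any test, and a common correlation between the paired differences, since the documents give none.

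**Error rate if any one significant result counts.** For k independent comparisons the rate is 1 − 0.95^k:

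- k = 1: 5.0%, the stated level
- k = 5: 1 − 0.95^5 = 22.6%
- k = 10: 1 − 0.95^10 = 40.1%

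Simulated paired t tests with n = 14 give:

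| Comparisons | correlation 0.5 | 0.7 | 0.9 |
|---|---|---|---|
| any of 5 | 18.8% | 15.5% | 10.6% |
| any of 10 | 30.0% | 22.5% | 13.5% |

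Five is the count with one score per test at one time. Ten arises with both post-gum times, or with two scores per test at one time. The ten-comparison row is illustrative only: it applies one correlation both to different tests and to the same test at two times.

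**Error rate if all five tests must be significant.** In the same simulations the rate is 0.06 / 0.33 / 1.49% at correlation 0.5 / 0.7 / 0.9. That holds when no test has an effect. If four tests had large true effects and one had none, the rate of declaring all five would approach 5%, but would not exceed it.

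**Error rate with Holm.** When no test has an effect, Holm over m tests makes a false claim only if the smallest p-value is at most 0.05/m.

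- Over five, independent: 1 − 0.99^5 = 4.9%; simulated 4.4 / 3.7 / 2.6% at correlation 0.5 / 0.7 / 0.9.
- Over five, but with the better of two times chosen afterwards, independent: 1 − 0.99^10 = 9.6% (9.4% in one simulation).
- Over all ten, independent: 1 − 0.995^10 = 4.9%.

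**Power** (noncentral t, paired, n = 14, two-sided):

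| Alpha | Difference detectable with 80% power | Power at 0.81 SD |
|---|---|---|
| 0.05 | 0.81 SD | 80% |
| 0.01 (Holm over 5, first step) | 1.05 SD | 53% |
| 0.005 (Holm over 10, first step) | 1.15 SD | 41% |

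SD here is that of the within-person CAF−PLA difference.

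**The case against.** The strongest reply is that the five tests measure different abilities (working memory, flexibility, inhibition of interference, visual search, abstract reasoning). The authors may intend five separate conclusions, and whether distinct domains need a joint correction is partly a matter of judgement. This stands in part: no passage says that one significant test is enough, so the inflation is conditional. It does not remove the point, because section 2.1 calls the tests collectively primary and nothing labels them exploratory.

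A second reply is that the analyses are not absent: each has a stated purpose. That is right. The defect is that their roles overlap and neither is ranked.

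A reader might go further and infer that the trial runs at a 23% or 40% false-positive rate. The documents do not support that: the rate depends on an unstated success rule, an unknown correlation and an unstated number of comparisons. Requiring all five tests would keep the error at or below 5%, though no such rule is stated either. Nor do the documents show that a test or time was selected after results were seen; they only leave room for it.

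**Conclusion.** The concern holds. The plan names a set of tests as primary but does not say which result, at which time, by which analysis, would establish a caffeine effect. That gap does not depend on any assumed number.

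The size of the error does. If any one significant test is read as a caffeine effect and there is none, the false-positive rate with five comparisons is about 23% if independent and about 11% at correlation 0.9, which is roughly two to four and a half times the nominal 5%. It is higher with more comparisons, reaching about 40% for ten independent ones. These figures assume two-sided paired t tests, n = 14 and a common correlation. Because the issue concerns the primary outcome, it must be fixed.

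**What to change.** First state whether results have been seen. Section 2.1 speaks of forwarding the data to a blinded analyst in the future, yet the Project summary already reports the fourteen participants' age, height and weight.

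- **Still blinded:** name one score per test (the displayed results would serve for four; for the Stroop, choose a condition or the interference score). Name one primary post-gum time and one primary analysis of the CAF−PLA contrast, and apply Holm across the five tests. Alternatively, name one sole primary test and make the rest secondary. Say which tests accuracy and hit reaction time belong to.
- **Results already seen:** apply Holm across every test, score and post-gum time that was available, which is at least ten comparisons, and label the choice post hoc. Holm over five with the time picked afterwards does not hold 5%.
- **Only test-by-test conclusions wanted:** say so, label them exploratory and make no overall claim.

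This needs no new data or participants. The cost is the loss of power shown above, so some nominally significant results may not survive. The sole-primary-test option avoids that loss for the chosen test.
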